## **Visit 2**

- Questionnaires regarding pain and fatigue will be provided for the subject to review and answer
- Standard-of-care lab draws will continue to occur. An additional 10 mL of blood will then be drawn for mitochondrial testing purposes.

## **Visit 3**

- Questionnaires regarding pain and fatigue will be provided for the subject to review and answer
- Standard-of-care lab draws will continue to occur. An additional 10 mL of blood will then be drawn for mitochondrial testing purposes.

	Control Group	NF1 Group			
		At time of Consent	Baseline/Visit 1	Visit 2 (14 weeks +/- 2 weeks)	Visit 3 (14 weeks +/- 2 weeks)
Medical History		X			
FACIT-F QoL		X	X	X	
Numeric Pain Rating QoL		X	X	X	
Research Lab – Blood	X	X	X	X	
SOC labs		X	X	X	

## **Study Population**

This study will look to enroll 40 to 45 adults over 18 years old diagnosed with NF1 as well as 10 to 15 adults over 18 years old without NF1 (the control group).

### **Inclusion Criteria**

#### **NF1 group**

- Over 18 years old
- Diagnosed with NF1
- Agreeable to participating in the study

#### **Control group**

- Over 18 years old
- Agreeable to participating in the study
- Not the first degree relative (biological parent, sibling, or child) of the NF1 patient who is in the NF1 group

### Exclusion Criteria

- NF1 group
  - Under 18 years old
  - Not agreeable to participating in the study
- Control group
  - Under 18 years old
  - Diagnosed with NF1
  - The first degree relative (biological parent, sibling, or child) of an NF1 patient who is participating in the study

Examples of recruitment methods include, but are not limited to the following:

- Patients with NF1 at the UAMS Adult NF1 clinic will be invited to participate in the study during their regular clinic appointments. If the patient is interested in participating in the study, a Cancer Clinical Trial Office nurse will be called to consent the patient.
- Spouses, friends, and non-relatives of NF1 patients who come to the UAMS Adult NF1 Clinic will be invited to participate in the control arm of the study at the time of the patient appointment. If the non-patient is interested in participating in the study, a Cancer Clinical Trial Office nurse will be called to consent the control group volunteer. They will then receive a single blood draw at the time of consent.

### **Risks and Benefits**

Risk is minimal as this is not an intervention study and the only procedure is collection of 10 mLs of blood. A blood draw can lead to discomfort, redness, bruising, or infection at the blood collection site.

The questions being asked by the FACIT-F and Pain Scales may cause patients to become sad or upset.

A risk to study subjects is the potential for loss of confidentiality of study data.

Measures to protect the confidentiality of study data will be implemented as described in the Data Handling and Recordkeeping section below.

There will be no direct benefits to the study participants; however, knowledge gained from the study could potentially benefit patients in the future.

### **Data Handling and Recordkeeping**

The Principal Investigator will carefully monitor study procedures to protect the safety of research subjects, the quality of the data, and the integrity of the study.

Paper Consents and paper forms will be stored at the Cancer Clinical Trials Office. A digital database for patient data entry will be developed by the Cancer Clinical Trials Office. The database will be housed on a UAMS-maintained server. All data will be coded with a unique identifying number upon entry into the database. The key to the code will be kept separately and maintained electronically on a password-protected computer. Only the PI and the study staff will have access to the key linking a patient's name to their data.

At the conclusion of the study, the samples and data will be indefinitely stored in a repository for future use. The key linking the samples and data to a subject's name will be retained indefinitely at the time of study closure in order to de-identify the data/samples.

If any patient desires to have their blood sample destroyed at any time during or after conclusion of this study, patient data will be decoded, and the sample will be destroyed upon the subject's request for withdrawal.

### **Specimen Handling and Storage**

Blood samples will be collected from patients and controls during routine appointments. Samples will be given a unique identifying number, and then transported to [name] laboratory where they will be tested and stored. A key linking the coded sample to the data will be maintained separately on a UAMS password-protected server. Transport will be done by Drs [name] laboratory staff.

If the patient sample volume is not completely used for this project, it will be retained for further study if patient indicates so in the consent. This sample might be used for future research to study the pathophysiology of neurofibromatosis. In the case that there is an opportunity to use the storage blood, we will decode data and enter in contact with patient to request their consent for the new project.

### **Data Analysis**

XF Pro mito-stress test data will provide direct measurements of basal, nonmitochondrial, and maximum respiration, and we will use these data to calculate the mitochondrial basal respiration, ATP-linked respiration, reserve respiratory capacity, proton leakage, and coupling efficiency in PBMCs and platelets isolated from the control group once and from NF1 patients longitudinally (3 times). At the end of each run, we will also determine the cellular bioenergetics and metabolic plasticity (switch between oxidative phosphorylation and glycolysis) of the cells via plotting extracellular acidification rate versus oxygen consumption rate. The NF1 and healthy control groups' mitochondrial function and metabolic plasticity parameters will be compared in addition to longitudinal changes in these parameters for each NF1 patient. Linear regression analysis will be utilized to establish the relationship between coupling efficiency, respiratory capacity (ATP-linked, reserve capacity etc.) as well as metabolic plasticity and NF1 clinical phenotype and biochemical scores for fatigue, pain, CK, cardiac function, BMI, and liver function. Analysis of variance for repeated measures will also be used to analyze changes in these parameters over time by each group (NF1 patients before and after Vitamin D and/or KOS administration).

This pilot study was designed to test the feasibility of our recruitment and implementation procedures and operational strategies. Preliminary data obtained from this pilot project will also be used to assess the variability of outcomes for power analysis of future larger studies. A biostatistician will be consulted during pilot data analysis and included in the team for statistical power calculations for future studies.

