attachment is confirmed, the cells will be then incubated in a non-CO2 incubator for 20 min at 37°C. The cellular bioenergetics of PBMCs or platelets will be determined by using a standard mitochondrial stress test as we previously published via consecutively injecting oligomycin, an uncoupler (FCCP), and the mitochondrial electron transport chain blockers antimycin A and rotenone into the wells as we previously published (30–37). Clinical repercussions of MD in NF1 will be measured through serial scores of fatigue and pain on the same days that PBMC and platelets are collected. Fatigue will be assessed through the Functional Assessment of Chronic Illness Therapy-Fatigue (FACIT-F). FACIT-F is the only fatigue scale that has been validated in dermatological and painful disease, as it is commonly used in neurological disorders (38). Pain will be assessed by the NRS-11 scale, as recommended by the patient-reported outcome group of the Response Evaluation in Neurofibromatosis and Schwannomatosis (REIS) (39). Other biochemical and metabolic functions to be followed will be CK, cardiac function through echocardiogram, body mass index, liver, and kidney function.

**Aim 2: Assess whether therapeutic interventions impact mitochondrial function and metabolic plasticity of circulating cells of NF1 patients.** We hypothesize that NF1 patients' inherent mitochondrial dysfunction makes them more responsive to therapeutic interventions resulting in further mitochondrial injury (e.g., by MEK inhibitors, including KOS) or improved function (e.g., by vitamin D). Most patients are vitamin D deficient so the standard of care involves supplementation that could improve mitochondrial function given its essential role in many related processes. Also, we will carry out an exploratory study on the potential adverse effects of KOS on adult NF1 patients who are beginning therapy during the study window. While promising in treatment, the use of this drug has a high incidence of significant adverse side effects like cardiotoxicity (30%). The cause for toxicity is unknown yet may involve further compromised mitochondrial function as reported for other similar tyrosine kinase inhibitors (40). The combination of these studies will provide a critical preliminary assessment of the sensitivity of the mitochondrial measures to patient interventions as well as the possible capacity to correlate with favorable or harmful outcomes.

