Subjects who present to the clinic and match the inclusion/exclusion criteria for either the NF1 or control group will be provided a copy of the consent for review. A thorough discussion of the consent will be provided by study staff. If the subject agrees to participate, the following will be completed at each of the 3 total visits required by the study. Each visit will occur at 14 weeks (+/- 2 weeks):

### Visit 1

- The subject's medical history will be gathered. This will include information regarding a subject's height, weight, medications used, vitamin D levels, kidney, liver, and heart function.
  - For control subjects, the PI will confirm that the subjects do not have NF1 by family history and physical exam.
- Questionnaires regarding pain and fatigue will be provided for the subject to review and answer.
- Standard-of-care lab draws will continue to occur.
- An additional 10 mL of blood will then be drawn for mitochondrial testing purposes.

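### The Aim 1 association is assigned to ordinary linear regression with no patient term or visit rule, although each NF1 patient contributes three same-day pairs of symptom and mitochondrial measurements

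*Combined protocol and SAP*

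**What the plan says.** Data Analysis assigns the symptom association to one method: "Linear regression analysis will be utilized to establish the relationship between coupling efficiency, respiratory capacity (ATP-linked, reserve capacity etc" and so on, against fatigue, pain, CK, cardiac function, BMI and liver function. It mentions no patient effect, visit selection, averaging or clustering adjustment.

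The data for fatigue and pain are repeated and paired. Under Aim 1 in Study Design and Procedures, clinical repercussions are measured by "serial scores of fatigue and pain on the same days that PBMC and platelets are collected". The visit description says that "the following will be completed at each of the 3 total visits required by the study", and the Visit 2 and Visit 3 lists each include the item "Questionnaires regarding pain and fatigue will be provided for the subject to review and answer" and a research blood draw. Data Analysis confirms that cells come "from NF1 patients longitudinally (3 times".

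A repeated-measures method is named, but for a different question: "Analysis of variance for repeated measures will also be used to analyze changes in these parameters over time by each group", with the groups explained as "NF1 patients before and after Vitamin D and/or KOS administration".

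On later statistical input, the section says "A biostatistician will be consulted during pilot data analysis".

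**The concern.** Three records from one patient are not three independent observations. The wording allows at least three analyses: pool all patient-visits, use one visit, or use one mean per patient. They differ in two ways.

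- **Error rate and power.** Pooling as independent understates the standard error whenever both variables are correlated within patient. One visit or patient means avoid this, but they do not have the same power.
- **What is estimated.** A pooled or single-visit slope mixes two associations: whether patients with poorer mitochondrial function have worse symptoms, and whether a given patient feels worse on visits when function is lower. Aim 1 reads mainly as the first.

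Two analysts following the text could therefore report different slopes and p-values from the same data on the study's main question, and the choice could be made after the results are visible.

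**Working it through.** **Inputs from the documents.** 40 to 45 NF1 patients (Study Population); m = 3 visits (visit description and Data Analysis). The Aim 1 text also speaks of sampling every 3-4 months for one year, which could mean more than three samples; three is used because two places state it outright. With complete follow-up there are 40 × 3 = 120 to 45 × 3 = 135 patient-visits.

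**Assumed, because the documents give no figure.** Two-sided alpha of 5%; the ICC of the mitochondrial parameter (ICCx) and of the symptom score (ICCy); equal correlation between any two visits. The plan has no figure of its own to reproduce.

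**Step 1: error rate if visits are pooled.** With no true association, the variance of the pooled slope is inflated by

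DE = 1 + (m − 1) × ICCx × ICCy,

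and the actual error rate is 2 × [1 − Φ(1.96 / √DE)]. For ICC 0.5 in both, DE = 1 + 2 × 0.25 = 1.50, 1.96 / √1.50 = 1.60, and the error rate is 11.0%. The formula was checked by simulation with at least 40,000 null datasets per setting.

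| ICCx / ICCy | DE | Formula | Simulated, n = 40 / n = 45 |
|---|---|---|---|
| 0 / 0.9 | 1.00 | 5.0% | 4.9% / 5.0% |
| 0.1 / 0.1 | 1.02 | 5.2% | 5.1% / 5.2% |
| 0.3 / 0.3 | 1.18 | 7.1% | 7.2% / 7.2% |
| 0.5 / 0.5 | 1.50 | 11.0% | 10.9% / 11.1% |
| 0.3 / 0.9 | 1.54 | 11.4% | 11.3% / 11.4% |
| 0.7 / 0.7 | 1.98 | 16.4% | 16.3% / 16.6% |
| 0.9 / 0.9 | 2.62 | 22.6% | 22.9% / 23.2% |

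The product of the two ICCs drives the result. One visit per patient, or the patient mean, gave 4.7% to 5.2% throughout.

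**Step 2: power of one visit against the three-visit mean.** Let rb and rw be the between- and within-patient correlations. The correlation that each analysis sees is

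- one visit: rb√(ICCx·ICCy) + rw√[(1 − ICCx)(1 − ICCy)];
- mean of three: {rb√(ICCx·ICCy) + rw√[(1 − ICCx)(1 − ICCy)] / 3} / √{[ICCx + (1 − ICCx)/3] × [ICCy + (1 − ICCy)/3]}.

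With n = 40 and rb = 0.5, simulated:

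| ICCs | rw | Correlation seen, one visit / mean | Power, one visit / mean |
|---|---|---|---|
| 0.5 / 0.5 | 0 | 0.250 / 0.375 | 35% / 68% |
| 0.9 / 0.3 | 0.5 | 0.392 / 0.431 | 72% / 81% |
| 0.5 / 0.5 | 0.5 | 0.500 / 0.500 | 92% / 92% |

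The Fisher approximation Φ(atanh(r) × √37 − 1.96) gives 34% / 67%, 71% / 80% and 92% / 92%, in agreement. Equal ICCs with equal correlations give no loss. With equal ICCs and rw above rb, one visit can even do slightly better, but by borrowing the within-patient association.

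**Step 3: what the slope estimates.** Take a true between-patient slope of 0.5, a within-patient slope of 0 and ICC 0.5. One visit gives 0.5 × 0.5 = 0.25; pooling gives about the same. The three-visit mean gives 0.5 × 3 × 0.5 / (1 + 2 × 0.5) = 0.375. Averaging reduces the dilution but does not remove it.

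**The case against.** The strongest reply is that this is a feasibility pilot with no stated alpha or decision rule, that a biostatistician will be consulted, and that the plan does recognise repeated measures. The first part lowers the stakes and stands. The consultation names no method and takes place during analysis. The repeated-measures ANOVA concerns change over time around vitamin D or KOS; it does not relate symptom scores to mitochondrial function.

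It is also fair that a mixed model is one valid choice among several, and that it adds tests. At least four parameters, six outcomes and two cell types already give 4 × 6 × 2 = 48 associations, and the model adds a second coefficient for each one with a repeated outcome. That is a reason to name one term as the main estimate.

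Three stronger readings are tempting, and the documents do not support them:

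- A reader might infer that the trial will run an inflated test. Pooling is nowhere stated; two of the three readings above hold 5%, and so does pooling if either ICC is near 0.
- A reader might infer that the variance estimates for future power analysis depend on this regression. Data Analysis says only that pilot data will be used for them. Three samples per patient allow both variance components to be estimated whichever regression is run.
- A reader might infer from the Visit 1 history that BMI and cardiac function are recorded only once. The Aim 1 text lists both among the functions to be tracked, so the two places need reconciling.

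**Conclusion.** The point holds as a gap in specifying the main Aim 1 analysis. Ordinary linear regression, as written, does not suit three paired records per patient unless the visits are reduced to one record, and the plan does not say that they are. The size is conditional: under pooling, about 5% to 23% error in place of an assumed 5%, for ICCs from 0.1 to 0.9 in both variables. The upper end needs 0.9 in both. Choosing one visit instead protects the error rate but can cost power substantially (35% against 68%), moderately (72% against 81%) or not at all, depending on ICCs and correlations that the documents do not give.

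The three pairs per patient are explicit only for fatigue and pain. For a pilot this is a matter to correct before the data are analysed; it does not undermine the design.

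**What to change.** In Data Analysis, for outcomes measured at every visit, replace the linear regression with a linear mixed model on all visits. Include a patient random intercept, a fixed visit effect, and two terms for the mitochondrial parameter: the patient's mean and the visit's deviation from it. Use small-sample degrees of freedom (Satterthwaite or Kenward-Roger). Name the patient-mean term as the main Aim 1 estimate, and note that a mean of three visits still attenuates that slope. If only the between-patient association is wanted, regress on patient means and say so.

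A simulated version of the mixed model, with fixed degrees of freedom (n − 2 between, N − n − 3 within, where N is the number of records), gave error rates of about 4% to 6% for both terms, with complete data or 20% of Visit 2 and 3 records missing. The Satterthwaite and Kenward-Roger versions were not simulated.

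Reconcile the Aim 1 text with the Visit 1 list on whether BMI and cardiac function are repeated. Use one prespecified record per patient only for outcomes recorded once.

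The cost is a few sentences, wider standard errors than pooling would give, and a second tested coefficient for each association with a repeated outcome. No extra patients, visits or blood are needed.

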The relation between neurofibromin and mitochondria is structural and functional. Neurofibromin can be co-localized within and extracted from mitochondria (26). Losing neurofibromin, guanosine-5'-triphosphate (GTP) hydrolysis decreases, activating RAS, a protein complex that stimulates mitochondrial degradation (27). Neurofibromin might also modulate mitochondrial respiration. Animal models showed mitochondrial respiration inhibition characterized by increased superoxide anion production and decreased adenosine triphosphate (ATP) generation that was reverted with transgene expression of neurofibromin (9). Loss of neurofibromin also activates extracellular signal-regulated-1/2 (ERK 1/2), affecting its interaction with mitochondrial chaperone tumor necrosis factor receptor associated protein 1 (TRAP1), decreasing succinate coenzyme Q reductase(10,27). Although NF1 animal models show mitochondrial dysfunction, literature evaluating mitochondrial function in patients with NF1 is scarce. Another factor possibly impacting mitochondrial function is the use of MEK inhibitors. These drugs are the only FDA-approved treatment for plexiform neurofibroma, a type of tumor that grows in the nerves of NF1 patients. MEK inhibitors can cause an increase in the oxygen consumption rate, and they can alter the mitochondrial metabolism affecting complex I and the electron transport chain (24,29). **We hypothesize that NF1 patients exhibit a range of MD that contributes to adverse health outcomes.** Validation of this hypothesis will establish a bioenergetic phenotype among NF1 patients to better stratify them than current clinical descriptions. This information will then be used for identifying relationships between patient symptoms and mitochondrial function to demonstrate its value in the clinic (Aim 1). Further, patient mitochondrial function will serve as an important mechanistic readout on the consequences of neurofibromin mutations and impacts of other factors including lifestyle, diet, and drugs (like MEK inhibitors) that can improve or harm mitochondrial function (Aim 2). These findings would expand beyond the current limitations of results from model neurofibromin knockout studies to more relevant complexities observed with patients. Taken together, information gained from patient mitochondrial function assessments would create opportunities to develop more personalized, targeted therapeutic interventions for improving patient outcomes.

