#### **Aim 1: Demonstrate mitochondrial respiration efficiency of PBMCs inversely correlates with clinical symptoms of NF1 patients.**

We will use an Agilent Seahorse XF Pro Analyzer to measure the cellular and mitochondrial bioenergetics of PBMC isolated from NF1 patients. We predict patients with milder symptoms of fatigue, pain, liver and cardiac function, creatine kinase (CK), and body mass index (BMI) will demonstrate better mitochondrial function in their circulating cells.

**Aim 2: Assess whether therapeutic interventions impact mitochondrial function and metabolic plasticity of circulating cells of NF1 patients.**

We hypothesize that MD among NF1 patients sensitizes them to therapeutic interventions targeting mitochondria. We will assess the impact of vitamin D treatment to potentially improve mitochondrial function and explore if MEK inhibitors like Koselugo (KOS, Selumetinib, FDA-approved treatment of plexiform neurofibromas in NF1) harm mitochondrial function in patients with NF1, due to their impact in the RAS pathway (24). We predict that the impact of treatments on mitochondrial function will lead to insights on mechanisms of action for NF1 patients and possibly serve as diagnostic and/or prognostic biomarkers for patient outcomes.

Preliminary findings will demonstrate a powerful, novel approach for assessing and understanding the differences in bioenergetic status among NF1 patients and open new research venues. The next steps will study the degree of MD and its correlation with 1) different NF1 mutations (deletions, truncations), 2) other NF1 complications like cognition outcome and quality of life, and 3) prevalence and prognosis of cancers.

Hence, this proposal will generate future projects that will aid the team in achieving the long-term goal of determining mechanisms driving NF1 clinical phenotypes and symptoms to stratify and treat patients. To that end, this pilot study will foster a collaborative team across disciplines and departments at UAMS to leverage the first and only neurofibromatosis clinic in Arkansas at UAMS for improving adult NF1 patient care, and also expand the spectrum of research done by the Drs. [name] and [name], who have not researched populations with genetic diseases so far, and [name], who has not researched mitochondrial function.

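### The Aim 1 regressions pool NF1 patients on and off a MEK inhibitor with no drug term, so drug exposure could distort the cardiac association in either direction

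*Combined protocol and SAP*

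**What the plan says.** **Who enters.** Study Population sets the size: "This study will look to enroll 40 to 45 adults over 18 years old diagnosed with NF1". The NF1 inclusion criteria are age, agreement to take part and "Diagnosed with NF1". The NF1 exclusions are age under 18 and "Not agreeable to participating in the study". Neither list mentions MEK-inhibitor use, and the Aim 2 text expects some patients to start the drug during the study.

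**What is regressed.** Under Data Analysis, "Linear regression analysis will be utilized to establish the relationship between coupling efficiency, respiratory capacity" and metabolic plasticity on one side, and "NF1 clinical phenotype and biochemical scores for fatigue, pain, CK, cardiac function, BMI, and liver function" on the other. No covariate, stratum or restriction is named. Drug exposure appears only in the next analysis, the repeated-measures ANOVA before and after vitamin D or selumetinib.

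**What the plan says about the drug.**
- Background and Rationale: "MEK inhibitors can cause an increase in the oxygen consumption rate, and they can alter the mitochondrial metabolism affecting complex I".
- Specific Aims, Aim 2: the study will "explore if MEK inhibitors like Koselugo (KOS, Selumetinib, FDA-approved treatment of plexiform neurofibromas in NF1) harm mitochondrial function".
- Study Design and Procedures, Aim 2: "the use of this drug has a high incidence of significant adverse side effects like cardiotoxicity (30" (the figure is a percentage). The same paragraph suggests that this toxicity may run through the mitochondria.

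**What is recorded.** Medications are part of the history taken at Visit 1. The lists for Visits 2 and 3 do not include them.

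**The concern.** Aim 1 is worded as a demonstration that poorer mitochondrial function goes with worse clinical status in NF1, and the Background wants to use the result to stratify patients. A variable that shifts both the mitochondrial measure and the outcome produces a correlation in pooled data even if none exists among treated or among untreated patients. For cardiac function, the plan itself supplies both halves of that mechanism: a hypothesised effect on mitochondria and a stated cardiac toxicity. If the two shifts run together, a drug effect (the subject of Aim 2) could be reported as the NF1 phenotype (the subject of Aim 1). If they run in opposite directions, a real NF1 association could be hidden.

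**Working it through.** The plan gives no alpha, effect size or sample-size calculation, so there is no figure to reproduce. The check asks how large the distortion could be.

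**Inputs from the documents.** 40 to 45 NF1 patients; 30% cardiotoxicity on the drug.

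**Assumptions, none of them in the documents.** Number treated, size of the shifts, two-sided 5% test, one sample per patient, and no association within treated or within untreated patients. Both measures are scaled so that higher is worse.

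**Formula, both measures shifted in every treated patient.** With share p treated, v = p(1 − p), a mitochondrial shift of a SD and an outcome shift of b SD:

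r = v·a·b / √[(1 + v·a²)(1 + v·b²)]

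With 9 of 45 treated, p = 0.2 and v = 0.16. For a = b = 1, r = 0.16/1.16 = 0.138. If b = 0, r = 0, so the drug must act on both sides. The critical |r| is 0.294 at n = 45 and 0.312 at n = 40.

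**Simulated rejection rates, n = 45, shifts on both measures.**

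| Treated | Shift, both (SD) | Mean r | No drug term | With drug term |
|---|---|---|---|---|
| 9 | 0.5 | 0.04 | 6% | 5% |
| 5 | 1 | 0.09 | 9% | 5% |
| 9 | 1 | 0.14 | 15% | 5% |
| 14 | 1 | 0.18 | 22% | 5% |

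**The cardiac case.** Only 30% of treated patients are shifted, by b SD. The covariance is v·a·0.3b. The outcome variance is 1 + p·(0.3)(0.7)b² + v(0.3b)². With 9 treated, a = 1 and b = 2:
- covariance = 0.16 × 0.6 = 0.096
- outcome variance = 1 + 0.168 + 0.0576 = 1.2256
- r = 0.096/√(1.16 × 1.2256) = 0.081

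Simulated rejection rates without a drug term:

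| Treated | a = 0.5, b = 2 | a = 0.5, b = 3 | a = 1, b = 2 | a = 1, b = 3 |
|---|---|---|---|---|
| 3 | 5% | 6% | 6% | 7% |
| 5 | 6% | 6% | 7% | 8% |
| 9 | 6% | 7% | 9% | 12% |

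With a drug term the rate is about 5% in every cell.

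**Opposite direction.** Suppose the drug improves the measured mitochondrial value by 1 SD and worsens the outcome by 1 SD, with 9 treated. Mean r is then −0.14. About 0.2% of trials are significant in the direction that Aim 1 predicts, against 2.5% by chance.

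**The case against.** A reader might infer that the plan says the drug affects both sides of every Aim 1 regression, and that drug exposure alone would therefore yield the predicted inverse correlation. The documents do not support that. The mitochondrial effect is a hypothesis to be explored. A drug effect on the outcome side is stated only for cardiac function. The Background also reports a rise in oxygen consumption, which could work against the predicted correlation.

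Four further objections carry weight.

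- **Size.** In the cardiac case most settings give 6% to 9%, barely above nominal. With 1 SD shifts and 9 treated, about 85% of trials would still show nothing significant. This stands, and it limits the force of the point.
- **Mediation.** If cardiotoxicity runs through mitochondria, low respiration alongside cardiac harm is a real association. A drug term then discards the drug-driven variation that carries it. This stands, and it is why the unadjusted result must be kept.
- **Restriction to off-drug samples.** Study Design and Procedures sets the goal as the association in NF1 patients as they are, not in untreated patients only. Dropping 9 or 14 of 45 would also cost power: for an assumed true r of 0.4, from about 79% to 69% or 63%. This stands against making restriction the main analysis.
- **Pilot status.** The study is a feasibility pilot, a biostatistician will be consulted during analysis, and linear regression does not rule out covariates. This softens the consequence. It does not remove the gap, because Aim 1 is worded as a demonstration and an adjustment chosen after seeing the data is weaker than one named in advance.

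**Conclusion.** The point holds with moderate confidence, chiefly for the cardiac regression. As written, that analysis can mix a drug effect with the NF1 association, and the plan does nothing to separate them. For fatigue, pain, CK, BMI and liver function the same mixing is plausible but undocumented.

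Under the stated assumptions the false-positive rate is about 5% to 12% in the cardiac case (3 to 9 treated). It is about 9% to 22% if every treated patient is shifted by 1 SD on both measures (5 to 14 treated). With few users or small shifts the distortion is slight. The direction cannot be settled from the documents, so neither a spurious correlation nor a masked one should be presumed.

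**What to change.** In Data Analysis, state that the Aim 1 regressions, the cardiac one above all, will be reported both without and with a term for MEK-inhibitor use at the time of the blood draw. Show the estimate from off-drug samples as a sensitivity analysis. Add that an association which disappears once the drug term is included will be read as possibly drug-related, through confounding or mediation, and not as the NF1 phenotype.

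The Visit 1 regression needs no new data, because medications are already collected there. If samples from Visits 2 and 3 are used, record drug status at each draw.

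Cost: a few sentences, one degree of freedom (residual 43 to 42 at n = 45), a slightly wider interval, and a one-line medication update at Visits 2 and 3.
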